	
information (PI) compared to a titrated dose, in combination with a basal insulin in adult subjects (≥ 18 years of age) with T1DM or T2DM.
 
Eligible subjects will be on a stable regimen consisting of a basal-bolus insulin therapy prior to screening.
 
The study is composed of up to 4 clinic visits (screening, 2 treatment visits, and a follow-up visit):
 
• Screening (Visit 1): Informed consent will be obtained and eligibility confirmed. Eligible subjects will be enrolled at Visit 1.• Visit 2: The first dose of Afrezza will be based on the dose of subcutaneous rapid-acting insulin analog (RAA) that the subject would normally take, converted according to the guidelines provided in the current Afrezza PI. If the subject's normal RAA dose is < 4 units, the subject will be asked to consume enough nutritional shake, per their normal insulin:carbohydrate ratio, to cover an RAA dose of ≥ 4 units such that their Afrezza dose at Visit 3 is higher than the dose taken at Visit 2. After completing the standardized meal challenge, the Investigator will decide, based on the subject's glucose excursion at Visit 2, if the subject should proceed to Visit 3 where a second dose of Afrezza will be administered.• Visit 3: The second dose of Afrezza will be based on the dose of subcutaneous RAA that the subject would normally take, converted by multiplying their RAA dose by 2 and rounding down to the nearest Afrezza cartridge size.• Follow-up (Visit 4): Subjects will return for safety assessments 24 to 72 hours after their last dose of Afrezza. 
Treatment Period
 
Subjects will come into the clinic in a fasting state for Visits 2 and 3, with exception of treating hypoglycemia. Fasting will be defined as no intake of drink or food, with exception of water, for ≥ 6 hours before the clinic visit. At the beginning of each visit, before their dose of Afrezza, subjects will have FEV₁ measurements taken in the clinic.
 
Before each dose of Afrezza, subjects will be trained on proper inhalation technique with BluHale® PRO.
 
Each meal challenge will consist of 1 to 2 bottles of nutritional shake to be fully consumed within 15 minutes. The nutritional shake will contain approximately 240 calories, 41 g carbohydrate, 10 g protein, and 4 g fat per bottle. Each Afrezza dose will be administered at the start of the meal challenge.
 
The subject's SMBG value must be between 100 and 200 mg/dL without requiring a correction dose of bolus insulin in order to receive the Afrezza dose and complete the meal challenge. Subjects

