1.2 Study Rationale

The current study aims to evaluate 2 different doses of Afrezza in adults ≥ 18 years of age. Subjects will administer an Afrezza dose based on the current prescribing information (PI) with a meal challenge, and then proceed to a second meal challenge where a second Afrezza dose will be administered based on the subject's RAA dose multiplied by 2 and rounded down to the nearest Afrezza cartridge size, subject to Investigator discretion.

Pooled Afrezza trial data suggests that subjects achieve similar glycemic control with a dose ratio of 1.5- to 2-fold the equivalent unit value of a SC insulin analog in head-to-head comparisons (Kendall et al. 2020, Grant et al. 2019). Thus, the Sponsor has chosen to evaluate 2 different doses of Afrezza to assess whether a higher dose results in improved postprandial glucose control.

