3.4.2 Dosage Schedule

Subjects will administer Afrezza at Visits 2 and 3, at the start of a meal challenge, according to the dosing guidelines provided in Section 3.5.2.2.1.1 (Visit 2) and Section 3.5.2.2.2.1 (Visit 3).

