3.5.2.2 Treatment Period

Subjects will come into the clinic in a fasting state for Visits 2 and 3, with exception of treating hypoglycemia. Fasting will be defined as no intake of drink or food, with exception of water, for ≥ 6 hours before the clinic visit.

Subjects must have an SMBG value between 100 and 200 mg/dL without requiring a correction dose of bolus insulin in order to receive each AfreZZa dose and complete the meal challenges.

Subjects using an insulin pump will be instructed to make sure their insulin pump is not in the automated insulin delivery mode for the 3 hours before and during treatment visits. Subjects will also be instructed not to inject correction doses of bolus insulin during the 6 hours immediately preceding each AfreZZa dose. If the subject requires a bolus insulin injection to correct hyperglycemia within the 6 hours prior to the scheduled visit, the meal challenge will need to be rescheduled. An SMBG measurement will be taken 15 minutes before the expected dose of AfreZZa so the Investigator can assess if the subject is within the required SMBG range (100 to 200 mg/dL). If the subject's SMBG value is <100 mg/dL, the Investigator can provide 15 g of fast-acting carbohydrates and remeasure SMBG after 30 minutes to determine if the subject should proceed to the meal challenge. The SMBG value obtained immediately before each dose of AfreZZa (t=0) will be used to determine if the subject can proceed to the meal challenge and will serve as the baseline value for that visit.

Each meal challenge will consist of 1 to 2 bottles of nutritional shake to be fully consumed within 15 minutes. The nutritional shake will contain approximately 240 calories, 41 g carbohydrate, 10 g protein, and 4 g fat per bottle. Each AfreZZa dose will be administered at the start of the meal challenge.

3.5.2.2.1 Visit 2

The following procedures will be performed at Visit 2:

- Record concomitant medications (see Section 3.4.7.2)
- Complete training on the AfreZZa inhaler using BluHale® PRO
- Measure and record FEV₁ before AfreZZa dose
- Take first dose of AfreZZa with standardized meal challenge according to Section 3.5.2.2.1.1
- Measure and record FEV₁ after completion of the meal challenge
- Record AEs
- Collect and review glucose meter data
- Record any hypoglycemic episodes (see Section 3.5.5.6)
- Provide discharge instructions to the subject

3.5.2.2.1.1 Standardized Meal Challenge and AfreZZa Dosing at Visit 2

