The AfreZZa dose to be taken at Visit 2 will be based on the dose of RAA that the subject would normally take, converted according to the guidelines provided in the current AfreZZa PI as shown in Table 3.

For AfreZZa doses exceeding 12 units, inhalations from multiple cartridges are necessary. To achieve the required total mealtime dose, subjects should use a combination of 4-unit, 8-unit, and 12-unit cartridges.

Table 3: Dose of AfreZZa at Visit 2

RAA Dose (Units)	AfreZZa Dose (Units)
Up to 4	4
5	8
6	
7	
8	
9	12
10	
11	
12	
13	16
14	
15	
16	
17	20
18	
19	
20	
21	24
22	
23	
24	

RAA=rapid-acting insulin analog (e.g., insulin aspart or insulin lispro)

Note: There is no maximum dose of AfreZZa and the required total mealtime dose may differ from the examples provided in this table.

The dose of AfreZZa will be administered at the start of the meal challenge. The subject must consume 1 to 2 bottles of nutritional shake within 15 minutes for the meal challenge and take SMBG measurements 15 minutes before their AfreZZa dose, immediately before administering the AfreZZa dose ($t=0$; baseline) and at 15, 30, 45, 60, 90, and 120 minutes after AfreZZa dosing. The subject will remain under clinical supervision for the 2 hours after their dose of AfreZZa.

If the subject is wearing a continuous glucose monitor (CGM), they will be asked to write down their CGM value every time they take an SMBG measurement in the clinic. These CGM values will be entered in the CRF completed at Visit 2.

After completing the standardized meal challenge, the Investigator will decide, based on the subject's glucose excursion at Visit 2 if the subject should proceed to Visit 3 where a titrated dose of AfreZZa will be administered according to [Table 4](#).

3.5.2.2.2 Visit 3

The following procedures will be performed at Visit 3:

- Record concomitant medications (see Section [3.4.7.2](#))
- Complete refresher training on the Afrezza inhaler using BluHale PRO
- Measure and record FEV₁ before Afrezza dose
- Take the dose of Afrezza with standardized meal challenge according to Section [3.5.2.2.1.1](#)
- Measure and record FEV₁ after completion of the meal challenge
- Record AEs
- Collect and review glucose meter data
- Record any hypoglycemic episodes (see Section [3.5.5.6](#))
- Provide discharge instructions to the subject

3.5.2.2.2.1 Standardized Meal Challenge and Afrezza Dosing at Visit 3

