The Afrezza dose to be taken at Visit 3 will be based on the dose of RAA that the subject would normally take, converted by multiplying their RAA dose by 2 and rounding down to the nearest Afrezza cartridge size as shown in [Table 4](#). If the subject's normal RAA dose is <4 units, the subject will be asked to consume enough nutritional shake, per their normal insulin:carbohydrate ratio, to cover an RAA dose of ≥ 4 units such that their Afrezza dose at Visit 3 is higher than the dose taken at Visit 2.

For Afrezza doses exceeding 12 units, inhalations from multiple cartridges are necessary. To achieve the required total mealtime dose, subjects should use a combination of 4-unit, 8-unit, and 12-unit cartridges.

Table 4: Dose of AfreZZa at Visit 3

RAA Dose (Units)	AfreZZa Dose (Units)
<4	4
4	8
5	
6	12
7	
8	16
9	
10	20
11	
12	24
13	
14	28
15	
16	32
17	
18	36
19	
20	40
21	
22	44
23	
24	48

RAA=rapid-acting insulin analog (e.g., insulin aspart or insulin lispro)

Note: There is no maximum dose of AfreZZa and the required total mealtime dose may differ from the examples provided in this table.

The dose of AfreZZa will be administered at the start of the meal challenge. The subject must consume 1 to 2 bottles of nutritional shake within 15 minutes for the meal challenge and take SMBG measurements 15 minutes before their AfreZZa dose, immediately before administering the AfreZZa dose (t=0; baseline) and at 15, 30, 45, 60, 90, and 120 minutes after AfreZZa dosing. The subject will remain under clinical supervision for the 2 hours after their dose of AfreZZa.

If the subject is wearing a CGM, they will be asked to write down their CGM value every time they take an SMBG measurement in the clinic. These CGM values will be entered in the CRF completed at Visit 3.

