5.2.2 Randomization

This study is an open-label, single-arm study (not randomized).

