5.2.10 Treatment Exposure and Compliance

Descriptive statistics will be used to summarize subject dosing information including the basal, bolus, and total insulin doses by visit.

A by-subject listing of study drug administration will also be provided.

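### The shake amount need not match between Visits 2 and 3, and the detailed dosing sections enlarge the meal for RAA <4 units only at the higher-dose visit

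*Combined protocol and SAP*

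**What the plan says.** **Meal size.** Section 3.5.2.2 states: "Each meal challenge will consist of 1 to 2 bottles of nutritional shake to be fully consumed within 15 minutes". Each bottle holds about 41 g of carbohydrate. The detailed dosing sections for Visit 2 (3.5.2.2.1.1) and Visit 3 (3.5.2.2.2.1) each repeat the instruction: "The subject must consume 1 to 2 bottles of nutritional shake within 15 minutes for the meal challenge". Neither refers to the amount taken at the other visit. The meal is called standardized throughout, but the term is not defined as the same amount within a subject.

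**The rule for small RAA doses.** If the usual RAA dose is below 4 units, "the subject will be asked to consume enough nutritional shake, per their normal insulin:carbohydrate ratio", enough to cover at least 4 RAA units, "such that their Afrezza dose at Visit 3 is higher than the dose taken at Visit 2". The synopsis and Section 3.1 give this rule in their Visit 2 item. Section 3.5.2.2.1.1 omits it and Section 3.5.2.2.2.1 contains it. Section 3.4.2 sends the reader to those two detailed sections for dosing.

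**Purpose and analysis.** Section 1.2 says two doses were chosen "to assess whether a higher dose results in improved postprandial glucose control". Section 5.2.2 describes an open-label, single-arm, non-randomized study, and the lower dose always comes first. Section 5.2.11 summarizes glucose descriptively by visit and time point, with no adjustment for the meal. Section 5.2.10 will "summarize subject dosing information including the basal, bolus, and total insulin doses by visit"; it does not mention the amount of shake.

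**The concern.** With one arm and a fixed order, Visit 2 against Visit 3 within a subject is the only information on dose. The two by-visit summaries, from about 20 completers, will be read side by side. Carbohydrate load drives the primary measure, the change in glucose over the 120 minutes after dosing. If the meal grows at the visit where the dose grows, the difference between visits reflects both.

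For subjects with RAA below 4 units this could follow from the protocol's own wording. A site that works from the detailed sections finds no enlargement rule for Visit 2 and finds one for Visit 3. The larger Visit 3 meal would push glucose up just when the higher dose is meant to bring it down, so a real benefit would tend to be hidden. The 120-minute hypoglycemia comparison between doses would be affected for the same reason.

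**Working it through.** The plan offers no figure to reproduce: the 20 completers are stated not to come from a statistical calculation. The check is arithmetic on the meal and on the two dose tables.

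**Inputs from the protocol**
- Carbohydrate per bottle: 41 g (3.5.2.2). Range: 1 × 41 = 41 g to 2 × 41 = 82 g.
- Visit 2 dose (Table 3): RAA up to 4 units gives 4 U.
- Visit 3 dose (Table 4): RAA below 4 units gives 4 U; RAA 4 gives 8 U.

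**Assumptions**
- r is the subject's usual RAA dose for one bottle. The protocol gives no distribution of r; 2 and 3 units are illustrations.
- The Visit 2 meal is one bottle when it is not enlarged.
- An enlarged meal covers exactly 4 RAA units at a constant insulin:carbohydrate ratio, and part-bottles are allowed.

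**Formulas**
- Shake needed to cover 4 RAA units: 4 × 41 / r grams.
- Change in insulin per gram: (Visit 3 dose / Visit 3 grams) / (Visit 2 dose / Visit 2 grams).

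**Rule applied at Visit 3 only**

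| r | Visit 2 | Visit 3 grams | Visit 3 dose | Ratio |
|---|---|---|---|---|
| 2 units | 41 g, 4 U | 4 × 41 / 2 = 82.0 | 8 U | (8/82) / (4/41) = 1.0 |
| 3 units | 41 g, 4 U | 4 × 41 / 3 = 54.7 | 8 U | (8/54.7) / (4/41) = 1.5 |

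**Rule applied at both visits, same enlarged meal.** The grams cancel, so the ratio is 8/4 = 2.0 for both values of r.

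**Sensitivity to part-bottles.** If only whole bottles are served, the case r = 2 is unchanged, since it already needs exactly two bottles. For r = 3, two bottles correspond to RAA 6, which Tables 3 and 4 convert to 8 U and 12 U. Enlarging at Visit 3 only gives (12/82) / (4/41) = 1.5. Enlarging at both visits gives 12/8 = 1.5. The ratio is then the same either way, and the problem is the doubled carbohydrate load at Visit 3 alone.

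**Limit of the rule.** Two bottles cover 4 RAA units only if the insulin:carbohydrate ratio is at most 82/4 = 20.5 g per unit. Below r = 2 the rule and the two-bottle maximum conflict.

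Insulin per gram is only an index of how far meal and dose move together. It is not an endpoint and does not convert to mg/dL from anything in the protocol.

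**The case against.** The strongest reply is that the Visit 2 rule is in the protocol, twice. The synopsis and Section 3.1 both put it under Visit 2, and Section 3.4.2 points to the detailed sections for dosing without setting Section 3.1 aside. A site that reads everything would enlarge the meal at both visits. The wording also leans toward one meal per subject: both doses derive from the same usual RAA dose, and the meal is called standardized. Finally, this is a small descriptive proof-of-concept study. Fixed order and the investigator's decision after Visit 2 on who proceeds already limit any causal reading.

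Much of this stands. The placement is an inconsistency between sections, not a rule missing from Visit 2 altogether, and equal meals would not cure the fixed order. But the sections nearest to the act of dosing give the opposite picture from Section 3.1. Even a site that enlarges at both visits is never told to use the same amount.

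A reader might infer two stronger claims that the documents do not support:
- *Meals will differ for subjects generally.* For RAA of 4 units or more the text permits unequal meals but does not prompt them, so no ratio is worked out for those subjects.
- *The amount consumed will not be recorded.* Section 5.2.10 does not list it, but the CRF and the site operations manual were not available, and Section 6.4.1 asks for source records of all pertinent observations.

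**Conclusion.** The point holds as a gap and an inconsistency that should be corrected. The protocol allows 41 to 82 g at each challenge with no requirement to repeat the amount. Read literally, its detailed dosing sections enlarge the meal for RAA <4 subjects only at the higher-dose visit. Under the stated assumptions, the rise in insulin per gram falls from 2.0-fold to 1.0 at a one-bottle RAA of 2 units, and from 2.0-fold to 1.5-fold at 3 units. The second figure depends on part-bottles being allowed.

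In those subjects the error would tend to mask a benefit of the higher dose. It would be wrong to infer that the study result as a whole is biased in that direction: the number of RAA <4 subjects, how sites would read the sections, and the effect in mg/dL are all unknown. The Visit 3 procedure list also cites the Visit 2 dosing section. That slip is clerical, because Section 3.4.2 and Table 1 give the right reference.

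**What to change.** 1. In Section 3.5.2.2, state that the shake amount (bottles and grams of carbohydrate) and the RAA dose it is based on are set and recorded at Visit 2 and repeated at Visit 3.
2. Put the RAA <4 rule in Section 3.5.2.2.1.1 so that it applies from Visit 2.
3. List the amount consumed by visit alongside the dosing data in Section 5.2.10.
4. Correct the Visit 3 procedure list to cite Section 3.5.2.2.2.1 (clerical).

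The cost is two or three sentences, one CRF field if it is not already there, and one listing column. The downside is slightly less meal flexibility at Visit 3; a subject who cannot repeat the amount becomes a protocol deviation.

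Two limits remain and need their own line in the protocol: subjects above 20.5 g per unit cannot reach 4 RAA units with two bottles, and RAA 5 converts to 8 U in both Table 3 and Table 4.

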3 INVESTIGATIONAL PLAN

3.1 Overall Study Design and Plan

MKC-TI-191 is a Phase 4, single-arm, multicenter clinical trial evaluating the efficacy and safety of Afrezza, administered according to the current Afrezza PI compared to a titrated dose, in combination with a basal insulin in adult subjects (≥ 18 years of age) with T1DM or T2DM.

Eligible subjects will be on a stable regimen consisting of a basal-bolus insulin therapy prior to screening.

The study is composed of up to 4 clinic visits (screening, 2 treatment visits, and a follow-up visit):

- **Screening (Visit 1):** Informed consent will be obtained and eligibility confirmed. Eligible subjects will be enrolled at Visit 1.
- **Visit 2:** The first dose of Afrezza will be based on the dose of SC RAA that the subject would normally take, converted according to the guidelines provided in the current Afrezza PI. If the subject's normal RAA dose is <4 units, the subject will be asked to consume enough nutritional shake, per their normal insulin:carbohydrate ratio, to cover an RAA dose of ≥ 4 units such that their Afrezza dose at Visit 3 is higher than the dose taken at Visit 2. After completing the standardized meal challenge, the Investigator will decide, based on the subject's glucose excursion at Visit 2, if the subject should proceed to Visit 3 where a second dose of Afrezza will be administered.
- **Visit 3:** The second dose of Afrezza will be based on the dose of SC RAA that the subject would normally take, converted by multiplying their RAA dose by 2 and rounding down to the nearest Afrezza cartridge size.
- **Follow-up Visit (Visit 4):** Subjects will return for safety assessments, including a final FEV₁ measurement, 24 to 72 hours after their last dose of Afrezza.

See Section 3.5 for information on the assessments to be performed at these visits.

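### At an RAA dose of 5 units, Tables 3 and 4 both give 8 units of Afrezza, so a subject whose normal dose is 5 gets the same dose at both visits

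*Combined protocol and SAP*

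**What the plan says.** Section 3.5.2.2.1.1 sets the Visit 2 dose from the RAA dose the subject would normally take, "converted according to the guidelines provided in the current AfreZZa PI as shown in Table 3". Table 3 gives 4 units for RAA doses up to 4, and 8 units for 5 to 8. Section 3.5.2.2.2.1 sets the Visit 3 dose from the same RAA dose, "converted by multiplying their RAA dose by 2 and rounding down to the nearest Afrezza cartridge size as shown in" Table 4, which gives 8 units for RAA 4 and 5, and 12 for 6 and 7.

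One group has a special rule. If the normal RAA dose is below 4 units, "the subject will be asked to consume enough nutritional shake, per their normal insulin:carbohydrate ratio" (Section 3.1), to cover an RAA dose of at least 4 "units such that their Afrezza dose at Visit 3 is higher than the dose taken at Visit 2". The synopsis and Section 3.1 place this rule under Visit 2. Among the detailed dosing sections, only the Visit 3 one (3.5.2.2.2.1) carries it.

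Both tables carry a note that "the required total mealtime dose may differ from the examples provided in this table", and Section 1.2 describes the second dose as "rounded down to the nearest Afrezza cartridge size, subject to Investigator discretion". The same section gives the reason for using two doses: "to assess whether a higher dose results in improved postprandial glucose control". Section 2.1 frames the primary objective around two different doses. Each meal challenge is 1 to 2 bottles of shake at about 41 g carbohydrate per bottle (Section 3.5.2.2).

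**The concern.** The extra-shake rule shows that the authors saw equal doses at the two visits as a problem and meant to prevent them. It is triggered only below 4 units, where both tables give 4. The tables also coincide at 5, and nothing in the protocol deals with that. A subject whose normal dose is 5 would attend a second meal challenge, described in Section 3.5.2.2.1.1 as using a titrated dose, and inhale the same 8 units again.

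Efficacy is reported as by-visit descriptive summaries of SMBG (Section 5.2.11) in all dosed subjects (Section 5.2.4). The comparison of visits is therefore the comparison of doses. A subject with the same dose at both visits contributes glucose values to both columns but nothing to the dose contrast, and no planned summary sets such subjects apart.

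**Working it through.** **Inputs.** Tables 3 and 4; the doubling-and-rounding rule in 3.5.2.2.2.1; cartridges of 4, 8 and 12 units (Table 1), so doses move in steps of 4; 41 g per bottle and 1 to 2 bottles per challenge, i.e. 41 to 82 g (3.5.2.2); 20 planned completers (5.2.3). Blank table cells are read as carrying the value above them.

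**Step 1: reproduce the tables.** Visit 2 dose = 4 × ceil(RAA/4), minimum 4. Visit 3 dose = 4 × floor(2 × RAA/4), with 4 for RAA below 4. These formulas reproduce every whole-unit row from 1 to 24 of both tables. Selected rows:

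| RAA | Visit 2 | 2 × RAA | Visit 3 | Ratio |
|---|---|---|---|---|
| 3 | 4 | 6 | 4 | 1.00 |
| 4 | 4 | 8 | 8 | 2.00 |
| 5 | 8 | 10 | 8 | 1.00 |
| 6 | 8 | 12 | 12 | 1.50 |
| 7 | 8 | 14 | 12 | 1.50 |
| 8 | 8 | 16 | 16 | 2.00 |
| 9 | 12 | 18 | 16 | 1.33 |
| 24 | 24 | 48 | 48 | 2.00 |

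**Step 2: count ties.** Among the 21 whole-unit doses from 4 to 24, only 5 ties. The other 20 rise by 4 to 24 units, with ratios from 1.33 to 2.0 (median 1.775). RAA 1 to 3 tie at 4 and 4; those are the subjects the extra-shake rule is written for. If fractional doses are allowed and Table 3 is read as rounding up (an assumption, since the tables list whole units), every dose above 4 and below 6 ties at 8 and 8.

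**Step 3: size.** Suppose k of 20 subjects with both visits are tied and the other 20 − k share the same mean contrast d. The average contrast is d × (20 − k)/20, a dilution of k/20: 0%, 5%, 10% and 15% for k = 0, 1, 2 and 3. The documents give no distribution of RAA doses, so k cannot be estimated.

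**Step 4: can a meal be sized to avoid 5?** Let ICR be the insulin:carbohydrate ratio in g per unit. The documents give no ICR values, so these are ranges.
- A normal dose of 5 that matches 41 to 82 g implies ICR from 41/5 = 8.2 to 82/5 = 16.4.
- Covering 4 units needs 4 × ICR g, which is at least one bottle when ICR ≥ 41/4 = 10.25. Over 10.25 to 16.4 this is 41 to 65.6 g.
- Below 10.25, covering 6 units needs 6 × ICR g. Over 8.2 to 10.25 this is 49.2 to 61.5 g.

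Both meals lie within 41 to 82 g, so every such subject has a workable option. The doses become 4 then 8, or 8 then 12. The meal moves to 4/5 = 0.8 or 6/5 = 1.2 of the one matching the normal dose.

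**The case against.** The strongest defence is that the tie is a true property of the rule being studied. Section 3.1 describes the trial as comparing prescribing-information dosing with a titrated dose. If doubling and rounding down gives no increase at 5, a comparison of the two rules should include that. The 8-unit dose is also 8/5 = 1.6 times the RAA dose, inside the 1.5- to 2-fold range cited in Section 1.2. This limits the harm. It does not remove the point: Sections 1.2 and 2.1 ask about a higher dose and two different doses, and at 5 units the Visit 2 dose is also 1.6-fold.

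The table note and Investigator discretion would let a site depart from 8 units at Visit 3, and the Investigator decides who proceeds to Visit 3. These permit a correction at 5 but do not state one.

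A reader might infer three stronger things that the documents do not support.
- That the low-dose rule sends subjects below 4 units to 5. Its purpose clause, "such that their Afrezza dose at Visit 3 is higher than the dose taken at Visit 2", rules that out for a site that reads the whole sentence. The threshold is loosely worded, not intended to allow 5.
- That carbohydrate rises with the dose because the detailed Visit 2 section omits the extra-shake rule. The synopsis and Section 3.1 place that rule at Visit 2, so the sections read together imply the larger meal at both visits. No sentence fixes a subject's amount across visits, but this calls for clarification and does not show that meals will differ.
- That tied subjects would be hidden. The by-subject dosing listing (5.2.10) and the individual data listings by subject, visit and time point (5.2.1) let them be found afterwards.

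**Conclusion.** The point holds. At RAA 5 the two tables give the same Afrezza dose, the only whole-unit tie from 4 to 24. A subject whose normal dose is 5 is not covered by the extra-shake rule and, if the tables are followed, receives 8 units twice. For subjects below 4 units the wording admits 5 although its purpose excludes it.

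The effect is small and of unknown frequency; it may be zero. The figure of about 5% dilution per tied subject assumes 20 subjects with both visits and an equal contrast in all the others. The analysis set is all dosed subjects, so the denominator could differ. The plan is descriptive, with no test or power calculation, so no error rate is affected. This is a stated rule that misses its own aim in one row, and it is worth correcting because the correction is cheap.

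**What to change.** 1. In the low-dose rule (synopsis, 3.1 and 3.5.2.2.2.1), replace the threshold of at least 4 units with exactly 4 units, or at least 6 units. Two bottles cannot cover 4 units when ICR exceeds 82/4 = 20.5 g per unit, so say what happens then.
2. For subjects whose normal dose is 5, size the meal at both visits to cover 4 units (4 then 8 units of Afrezza) when that needs at least one bottle, i.e. ICR of at least 10.25 g per unit. Otherwise size it to cover 6 units (8 then 12). A fixed order is needed because both options fit for ICR from 10.25 to 82/6 = 13.7.
3. As a clarification, state that each subject drinks the same amount of shake at Visits 2 and 3, repeat the extra-shake rule in 3.5.2.2.1.1, and record the amount.

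An SMBG summary limited to subjects whose dose rose, beside the all-dosed summary, is optional and uses data already planned.

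The cost is a few sentences and one recorded value per visit. Part-bottles must be measured, and a 5-unit subject's meal moves 20% down or up from the one matching the normal dose.

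### A mealtime RAA dose of 5 units converts to 8 units of Afrezza at both visits, and the rule meant to make the second dose higher does not cover it

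*Combined protocol and SAP*

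**What the plan says.** The Visit 2 dose is the subject's usual RAA dose "converted according to the guidelines provided in the current AfreZZa PI as shown in Table 3" (3.5.2.2.1.1). The Visit 3 dose starts from the same RAA dose, "converted by multiplying their RAA dose by 2 and rounding down to the nearest Afrezza cartridge size", as laid out in Table 4 (3.5.2.2.2.1).

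For low doses there is a meal-size adjustment. If the "normal RAA dose is <4 units, the subject will be asked to consume enough nutritional shake" to bring RAA to at least 4 units, "such that their Afrezza dose at Visit 3 is higher than the dose taken at Visit 2". This rule appears in the synopsis and in 3.1 (both under Visit 2), and in 3.5.2.2.2.1.

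Meal size is bounded in 3.5.2.2: "Each meal challenge will consist of 1 to 2 bottles of nutritional shake to be fully consumed within 15 minutes". Each bottle holds "approximately 240 calories, 41 g carbohydrate, 10 g protein, and 4 g fat per bottle".

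Section 1.2 gives the reason for using two doses: "to assess whether a higher dose results in improved postprandial glucose control". Section 3.1 describes the study as Afrezza "administered according to the current Afrezza PI compared to a titrated dose".

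**The concern.** The sponsor anticipated that rounding to cartridge sizes could leave the two doses equal, and wrote a rule to prevent it below 4 units. The two conversions round in opposite directions: the Visit 2 table rounds up to the next 4 units, and the Visit 3 rule doubles and rounds down. That can produce a tie above 4 units as well, where the rule does not apply.

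A subject given the same dose twice contributes no dose contrast to the question in 1.2. The efficacy summary (5.2.11) presents SMBG by visit, so visit stands in for dose. In a tied subject, any difference between visits reflects something other than dose. The tie can be seen afterwards in the dosing listing (5.2.10), but by then it cannot be repaired.

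**Working it through.** **Inputs.** Table 3 (3.5.2.2.1.1); Table 4 and the doubling rule (3.5.2.2.2.1); cartridge strengths of 4, 8 and 12 units (Table 1); about 41 g carbohydrate per bottle and 1 to 2 bottles per meal (3.5.2.2). The RAA dose is taken to be the dose for the planned meal.

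**Step 1: reproduce the plan's tables.** Visit 2 dose = 4 x ceiling(RAA/4), minimum 4. Visit 3 dose = 4 x floor(2 x RAA/4), minimum 4. These formulas match every printed row for RAA 4 to 24, so both tables follow their stated rules.

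**Step 2: compare the two doses.**

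| RAA (units) | Visit 2 | Visit 3 | Difference |
|---|---|---|---|
| 1 to 3 | 4 | 4 | 0 |
| 4 | 4 | 8 | 4 |
| 5 | 8 | 8 | 0 |
| 6 to 7 | 8 | 12 | 4 |
| 8 | 8 | 16 | 8 |
| 9 | 12 | 16 | 4 |
| 10 to 11 | 12 | 20 | 8 |
| 12 | 12 | 24 | 12 |
| 13 to 24 | 16 to 24 | 24 to 48 | 8 to 24 |

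For whole units, the only ties are RAA below 4, which the meal adjustment addresses, and RAA 5, which it does not.

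**Step 3: fractional RAA.** No rounding rule is given. Assume Table 3 is read upward, so that 4.5 uses row 5. The Visit 2 dose is then 8 for any RAA above 4 and up to 8, and the Visit 3 dose is 8 for any RAA from 4 to just below 6. Every value above 4 and below 6 therefore ties at 8 and 8.

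**Step 4: the conditional case below 4 units.** Treat two bottles as a hard cap: 2 x 41 = 82 g. RAA cannot reach 4 units when the insulin:carbohydrate ratio exceeds:

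- 82/4 = 20.5 g/unit, if RAA is unrounded or rounded down;
- 82/3.5 = 23.4 g/unit, if rounded to the nearest unit;
- 82/3 = 27.3 g/unit, if rounded up.

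Beyond the limit the dose is 4 units at both visits at any permitted volume.

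**Step 5: can meal volume remove the ties?** For a subject who doses by ratio, yes, up to the Step 4 limits: under each convention some volume from 41 to 82 g gives a higher Visit 3 dose. Two examples:

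- At 16 g/unit, 80 g gives RAA 80/16 = 5 (8 then 8 units), and 64 g gives RAA 64/16 = 4 (4 then 8).
- At 8.2 g/unit, one bottle gives RAA 41/8.2 = 5 (8 then 8). Raising the meal to 49.2 g gives RAA 6 (8 then 12). Two bottles would also work, but they give RAA 10 (12 then 20), a much larger change.

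Part bottles matter. With whole bottles only, no volume works at these ratios either (band edges approximate):

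- nearest unit: 82/5.5 = 14.9 to 82/4.5 = 18.2 g/unit;
- rounded down: 82/6 = 13.7 to 82/5 = 16.4 g/unit;
- rounded up: 82/5 = 16.4 to 82/4 = 20.5 g/unit;
- unrounded: 82/6 = 13.7 to 82/4 = 20.5 g/unit.

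A subject on a fixed mealtime RAA of 5 ties at any volume.

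**Step 6: size.** The documents give no distribution of RAA doses or ratios, so the number affected cannot be computed. Each affected subject is 1/20 = 5% of planned completers.

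**The case against.** The strongest reply is that the plan prints these outcomes openly. Table 4 carries a row giving 4 units below RAA 4, directly beneath the meal-size rule, which suggests that some ties were foreseen. The RAA 5 result is what doubling and rounding down produces. The higher-dose wording is attached only to subjects below 4 units, and 3.1 can be read as comparing two dosing rules, in which case a tie is a genuine result of the second rule. This stands in part: it is a reason to keep tied subjects in the summaries. It does not explain why a tie should be prevented at RAA 3 and allowed at RAA 5 when 1.2 asks about a higher dose.

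A second reply is investigator discretion. Section 1.2 makes the second dose subject to it, and the table notes say doses may differ from the examples. These permit a departure but do not require anyone to check that the doses differ. The decision to proceed to Visit 3 rests on the Visit 2 glucose excursion. A site following both tables exactly gives 8 units twice at RAA 5.

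Third, the case below 4 units depends on precedence. The instruction to drink enough shake to reach 4 units could be taken to override the 1-to-2-bottle limit. The dosing sections say the subject must consume 1 to 2 bottles, which favors a cap, but precedence is not stated. That case is therefore conditional, and 20.5 g/unit is only the lower end of its limit.

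Four stronger inferences are not supported:

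- That the dose tables are wrong: they follow their own rules.
- That the adjustment is missing at Visit 2: 3.1 and the synopsis place it there.
- That an adjusted meal may land on RAA 5 unnoticed: the sentence asks for a volume that makes the Visit 3 dose higher.
- That the efficacy analysis is invalid: it is descriptive and by visit, with no test or planned paired comparison, and the sample size was not set statistically (5.2.3).

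**Conclusion.** The gap at RAA 5 is real and follows directly from the printed tables: 8 units at both visits, with the only safeguard triggered below 4 units. Unrounded, the gap covers every value above 4 and below 6, assuming Table 3 is read upward. The tie below 4 units is secondary. It holds only if two bottles is a hard cap, and only above 20.5, 23.4 or 27.3 g/unit depending on rounding, with about 41 g per bottle.

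The consequence is limited to lost dose contrast in the affected subjects, whose number is unknown and may be zero. A reader might infer that tied subjects should be excluded. The documents do not support that: 5.2.4 includes everyone dosed, and a tie is informative if the comparison is between dosing rules. The sponsor should make the change because it serves the protocol's own stated aim at little cost.

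**What to change.** In the synopsis, 3.1 and 3.5.2.2.2.1, replace the trigger of RAA below 4 units with a check made before Visit 2: for the planned meal, with RAA rounded by one stated rule, does the Table 4 dose exceed the Table 3 dose? If not, use the smallest change in shake volume within 1 to 2 bottles that makes it so. Allow part bottles and use the same volume at both visits. Asking for the smallest change keeps the meal and the insulin dose close to what they would otherwise have been, which matters because severe hypoglycemia is an identified risk (1.3).

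Where no permitted volume works, or a fixed mealtime dose ties, flag the equal-dose pair in the dosing listing (5.2.10) and keep the subject in the planned by-visit summaries. A supplementary SMBG summary of subjects whose doses differ is optional, because 5.2.1 already provides individual listings by subject, visit and time point. Repeating the rule in 3.5.2.2.1.1 would be an editorial convenience.

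The cost is one check before dosing, one sentence on rounding and one flag. The downside is a somewhat different meal size for a few subjects. Dose tables, eligibility and the analysis population are unchanged.
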